# 5. OBJECTIVE(S)

The primary, secondary, and safety objectives of this study are listed as follows.

# 5.1 **PRIMARY OBJECTIVE**

The primary objective of this study is to demonstrate clinical success of the ENTACT (Next

Generation) resorbable septal staple system by examining the patient's nasal cavity at the 21

day follow up visit.

This document contains information that is confidential and proprietary to Smith + Nephew PLC and Smith + Nephew, Inc. and is intended for use only by Smith + Nephew and its manufacturer. It shall not be reproduced or copied in whole or in part, nor shall the contents be disclosed by any means without prior written permission from Smith + Nephew, nor shall anyone make any use of it that is contrary to the expressed or implied wishes of Smith + Nephew.

Study Protocol	> ∕ smith&nephew
A prospective, multi-center, single arm PMCF study to evaluate the safety and performance of ENTACT ™ (Next Generation)	Number: ENTACT.ENT.PRO.SEP.2019.05
resorbable septal staple system for septoplasty	Version: 2.0, 27Aug2020
	Page: Page 27 of 94

# 5.2 **SECONDARY OBJECTIVE:**

The secondary objectives are to generate performance and health economics supporting the use of ENTACT (Next Generation) resorbable septal staple.

# 5.3 **SAFETY OBJECTIVE(S)**

Assess safety with reported complications, adverse events, adverse device effects, unanticipated serious adverse device effects, and device deficiencies (DD).

# 5.4 **CLAIMS**

The proposed Marketing Claims for this study include, but are not limited to, the following:

- Approximation of septal flaps is achieved in less than a minute;
- ENTACT septal stapler saves time in the operating room compared to traditional suturing techniques.

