# 4.2.1 Performance

Improvement in clinical outcome scores with the ENTACT Septal Stapler are reported in **Table 4.2.1-1**.

Indication	Author, Year	# of Pts	Septal Coaptation n (%)	Nasal Obstruction Symptom Evaluation (NOSE)		
				Pre-op	Post-op	Δ
Septoplasty	Sainio  ,2019	101	-	-	-	-
Open septoplasty plus turbinoplasty	Sowerby⁵, 2013	8	-	12	2	10
Septoplasty	Tami  , 2010	24	24 (100%)	-	-	-
Septoplasty	Yildirim  , 2013	20*	-	-	-	5.7 ± 0.923
*Estimated number of patients $\Delta$ Change from preop to postop scores						

Table 4.2.1-1. ENTACT Septal Stapler Clinical Outcome Scores

Approximately 153 patients have undergone septoplasty using the ENTACT Septal Stapler in four studies Sowerby et al. conducted a prospective randomized study and reported a significant decrease in the mean operation time in the ENTACT Septal Stapler group compared to the quilting sutures group (28 ± 6 minutes vs. 43 ± 13 minutes respectively; p=0.014). The mean time for septal closure was also reported to be significantly lower in the ENTACT Septal Stapler group than the quilting suture group (35 ± 22 seconds vs. 420 ± 70 seconds; p<0.001). In a prospective case series conducted by Tami et al. the amount of time taken to apply staples from the ENTACT Septal Stapler was reported to be <60 seconds. Sainio et al. conducted a retrospective comparative study comparing ENTACT Septal Stapler to the non-stapler group where silicone splints, tamponade, or sutures were used during septoplasty.

This document contains information that is confidential and proprietary to Smith + Nephew PLC and Smith + Nephew, Inc. and is intended for use only by Smith + Nephew and its manufacturer. It shall not be reproduced or copied in whole or in part, nor shall the contents be disclosed by any means without prior written permission from Smith + Nephew, nor shall anyone make any use of it that is contrary to the expressed or implied wishes of Smith + Nephew.

Study Protocol	>{ smith&nephew
A prospective, multi-center, single arm PMCF study to evaluate	Number:
the safety and performance of ENTACT™ (Next Generation)	ENTACT.ENT.PRO.SEP.2019.05 Version: 2.0. 27Aug2020
Tesol Dable Septal Staple System for Septoplasty	Page: Page 22 of 94

ENTACT Stapler group and the non-stapler group (63.9 minutes vs. 64.3 minutes, respectively).

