## 7.3 Exclusion Criteria

The patient will be ineligible for the study if he or she meets any of the following exclusion criteria at the baseline screening or during surgery:

- 1. Prolonged tissue approximation beyond that needed for normal tissue closure is necessary or desired;
- 2. Traditional suturing techniques is necessary;
- 3. Radiopacity is necessary or desired since ENTACT septal staples are radiotransparent;
- 4. Known to be allergic to foreign body of materials of investigational product;
- 5. Concomitant procedures other than turbinectomy, turbinate reduction and/or sinus surgery;
- 6. Pregnancy at time of procedure;
- 7. Presence of infection at the site;
- 8. Severe drug and alcohol abusers;
- 9. Autoimmune disease deemed clinically significant by Principal Investigator.

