# 8. STUDY DESIGN

# 8.1 STUDY DESIGN

This is a prospective, multi-center, single arm PMCF study to evaluate the safety and performance of the ENTACT (Next Generation) resorbable staple system for septoplasty in 40 subjects. The study purpose is to provide evidence to satisfy the PMCF requirements of CE Marking to market this device in Europe (data may be used to support registrations on other countries as well).

This study will enroll at up to 3 clinical sites in the United States.

This document contains information that is confidential and proprietary to Smith + Nephew PLC and Smith + Nephew, Inc. and is intended for use only by Smith + Nephew and its manufacturer. It shall not be reproduced or copied in whole or in part, nor shall the contents be disclosed by any means without prior written permission from Smith + Nephew, nor shall anyone make any use of it that is contrary to the expressed or implied wishes of Smith + Nephew.

Study Protocol	% smith&nephew	
A prospective, multi-center, single arm PMCF study to evaluate the safety and performance of ENTACT™ (Next Generation) resorbable septal staple system for septoplasty	Number: ENTACT.ENT.PRO.SEP.2019.05	
	Version: 2.0, 27Aug2020	
	Page: Page 42 of 94	

This is an open-label study with consecutive enrollment. The study will continue for 6 weeks from the date that the last subject received the study treatment to the date that the last subject completes the study as planned. Only subjects who meet the enrollment criteria as listed in **section 7** will be enrolled in the study. The study duration is an estimated 8 months from first study site initiation to last subject last visit.

Figure 8.1-1: Study Flowchart

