## 8.2 ALLOCATION AND BLINDING

### 8.2.1 Treatment Allocation

This study is not randomized. Subjects will be enrolled with the ENTACT (Next Generation) Septal Stapler system.

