### 8.3.2 Secondary Endpoints

- At the 5, and 42-day follow-up visit, the clinician will examine the patient's nasal cavity and will confirm:
  - Septum wall straight appearance (yes/no);
  - Complete coaptation of perichondrial flaps on septum wall (yes/no);

This document contains information that is confidential and proprietary to Smith + Nephew PLC and Smith + Nephew, Inc. and is intended for use only by Smith + Nephew and its manufacturer. It shall not be reproduced or copied in whole or in part, nor shall the contents be disclosed by any means without prior written permission from Smith + Nephew, nor shall anyone make any use of it that is contrary to the expressed or implied wishes of Smith + Nephew.

Study Protocol	% smith&nephew	
A prospective, multi-center, single arm PMCF study to evaluate the safety and performance of ENTACT™ (Next Generation) resorbable septal staple system for septoplasty	Number: ENTACT.ENT.PRO.SEP.2019.05	
	Version: 2.0, 27Aug2020	
	Page: Page 44 of 94	

- Absence of significant local tissue reaction at the staple site (yes/no);
- Absence of hematoma swelling at the staple site (yes/no);
- No need for re-intervention at the surgery site (yes/no);
- Assess the following intra-operative times for full population and by sub-groups of Septoplasty only cases and Septoplasty and turbinate reduction cases:
  - Total operation time for the procedure: Recorded as time between start of the procedure and when the drapes are removed from the patient, recorded in minutes
  - Time for operative closure with ENTACT Septal stapler: Recorded as time between start of closure to when the stapler was handed back to the scrub nurse, recorded in seconds.
- NOSE score collected at pre-op and all post-operative visits;
- VAS pain collected at pre-op and all post-operative visits.

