#### CONFIDENTIAL AND PROPRIETARY

Study Protocol	Smith&nephew
A prospective, multi-center, single arm PMCF study to evaluate the safety and performance of ENTACT ™ (Next Generation) resorbable septal staple system for septoplasty	Number: ENTACT.ENT.PRO.SEP.2019.05
	Version: 2.0, 27Aug2020
	Page: Page 81 of 94

4.4.1 Tolerance limits for potential adverse		Based on the state of the art data in Table 4.2.2-1 and Section 4.2.2 the expected tolerance limits for potential adverse effects from literature in the ENTACT Septal Stapler are the stated in Table 4.4.1-1 Table 4.4.1-1. ENTACT Septal Stapler Tolerance Limits	
effects derived from literature		Expected Complications       Tolerance limits       Tolerance limits to show no significant difference from literature! (maximum allowed)         Perforation       2/153 (1.31%)       2/40 5% (95% C1 0.6% to 16.92%)         Hematoma       1/153 (0.65%)       2/40 5% (95% C1 0.6% to 16.92%)         Inflammation       5/153 (3.27%)       4/40 10% (95% C1 2.8% to 23.7%)         Inflammation       5/153 (3.27%)       4/40 10% (95% C1 2.8% to 23.7%)         Inflator       6/153 (3.92%)       4/40 10% (95% C1 2.8% to 23.7%)         Actual study adverse events occurrences will be reviewed under Section 10.5 and Section 12 and assessed relative to the tolerance limits.         Actual study adverse events occurrences will be reviewed under Section 10.5 and Section 12 and assessed relative to the tolerance limits.	
		Section 10.5 and Section 12 and assessed relative to the tolerance limits.	
5.4 Claims	
 
Increased distance between both the distal ends for accommodating broader range of anatomies;
 
Overall, approximately 30% reduction in the distal arm volume for improved posterior access.
 
	Removed claims- data not collected in this study	
7.1 Subject Population	A minimum of 30 and maximum of 40 individuals to be approached for participation in this study and will include adult patients (ages 18 and over) who are receiving or seeking care for nasal septal obstructions. Subjects will be enrolled up to 3 sites across the United States.	Forty (40) individuals to be approached for participation in this study who are receiving or seeking care for nasal septal obstructions. Subjects will be enrolled up to 3 sites across the United States.	

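### Section 5.4 lists operating-room time saved against suturing as a claim for this study, which collects no suture times; its under-a-minute claim is testable but has no matching analysis

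*Combined protocol and SAP*

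**What the plan says.** Section 5.4 puts forward two marketing claims for the study. One is comparative: "ENTACT septal stapler saves time in the operating room compared to traditional suturing techniques". The other is absolute: "Approximation of septal flaps is achieved in less than a minute".

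The design is described in Section 8.1 ("This is a prospective, multi-center, single arm PMCF study to evaluate the safety and performance of the ENTACT") and Section 8.2.1 ("This study is not randomized. Subjects will be enrolled with the ENTACT (Next Generation) Septal Stapler system"). Section 7.3 excludes patients in whom suturing is needed, and its criteria apply at screening and also during surgery. It allows turbinate and sinus procedures: the exclusion reads "Concomitant procedures other than turbinectomy, turbinate reduction and/or sinus surgery".

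Section 8.3.2 defines two times. Total operation time runs from the start of the procedure to removal of the drapes. Closure time is "Recorded as time between start of closure to when the stapler was handed back to the scrub nurse, recorded in seconds". Section 10.4.2 summarises both descriptively, by septoplasty alone and septoplasty with turbinate reduction. It names no comparator, benchmark, test or 60-second criterion. Section 10.1 defines a continuous summary as n, mean, median, SD, minimum and maximum.

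The same Section 10.4.2 reports successful staple deployment with a Clopper-Pearson interval, plus staple count and misfires, but does not tie any of these to the closure time.

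Section 21.1.4 records that two other claims were dropped from Section 5.4, with the note "Removed claims- data not collected in this study".

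**The concern.** A claim of time saved against suturing is a difference between two quantities, and this study measures only one of them. A reader of Section 5.4 would expect the study report to contain the comparison. The only route to it would be a historical figure picked after the data are in, and the protocol does not say which.

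The under-a-minute claim is about flaps being approximated, whereas the recorded time stops when an instrument changes hands. The definition does not say what to record if delivery fails, a second stapler is opened, or sutures are added. A mean or median below 60 seconds would also not tell a surgeon how often closure takes under a minute.

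At stake is the credibility of two promotional statements that would cite a study meant to support CE marking. The primary endpoint and the safety analysis are not affected.

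**Working it through.** **No figure of the plan's own to reproduce.** Section 11 sizes the study for the precision of the success proportion. It gives nothing for operation or closure time.

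**Suturing claim: what each side supplies.**

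| Needed | In this study |
|---|---|
| Stapler times | Yes (8.3.2) |
| Suture times | None: one arm (8.1, 8.2.1), suture cases excluded (7.3) |
| Named historical comparator | None (10.4.2) |
| Test or interval for a difference | None (10.4.2) |

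The difference is not estimable from the study's own data.

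**Outside evidence, all in Section 4.2.1 and all on earlier generations.**
- Randomized study, 8 stapler patients, against quilting sutures. Operation time is 28 (SD 6) against 43 (SD 13) min: 43 − 28 = 15 min saved. Closure time is 35 (SD 22) against 420 (SD 70) s: 385 s, or 385/60 = 6.4 min saved. The suture group size is not given. Assuming 8 there too, Welch t = 15/√(36/8 + 169/8) = 2.96, p = 0.014, which agrees with the cited p-value.
- Retrospective study, 101 stapler patients: "ENTACT Stapler group and the non-stapler group (63.9 minutes vs. 64.3 minutes, respectively", so 64.3 − 63.9 = 0.4 min. The comparison group mixes silicone splints, tamponade and sutures. The start of this sentence is missing from the available text, so exactly what was timed cannot be read.

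**What a concurrent suture arm would take** (illustration; two-sided 5%, 80% power). Pooled SD = √((36 + 169)/2) = 10.1 min. Per arm, n = 2(1.96 + 0.84)²·SD²/d².
- d = 15 min: 8 per arm.
- d = 6.4 min: 40 per arm (14 to 65 for SD 6 to 13).
- d = 0.4 min: about 10,000 per arm.

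The plan has no suture arm, and the requirement depends entirely on which outside figure is believed.

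**Under-a-minute claim.** Assume closure times resemble the cited 35 (SD 22) s.
- The mean: 95% half-width = t(0.975, n − 1)·22/√n, which is 7.4 s at n = 36 and 7.0 s at n = 40. The upper limit at n = 40 is about 42 s, so a mean below 60 s could be shown.
- Single cases, normal shape: P(T < 60) = Φ((60 − 35)/22) = Φ(1.14) = 0.872.
- Single cases, lognormal shape: σ² = ln(1 + (22/35)²) = 0.333 and μ = ln 35 − σ²/2 = 3.389. Then P(T < 60) = Φ((4.094 − 3.389)/0.577) = 0.889.
- So 11 to 13% of closures would exceed 60 s.
- The planned maximum would settle the matter only if every case were under 60 s. In 40 cases the chance is 0.872⁴⁰ = 0.004 to 0.889⁴⁰ = 0.009.
- What a proportion would give: about 35 of 40 expected (40 × 0.872 = 34.9), Clopper-Pearson 73.2% to 95.8%. With 40 of 40 the interval is 91.2% to 100%.

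**Sensitivity to the end of the clock.** Suppose k of 40 deliveries fail, each is handed back at 35 s, and each then needs 420 s of suturing. The mean to actual closure is ((40 − k)·35 + k·455)/40. For k = 2 it is 56.0 s; for k = 3 it is 66.5 s. The hand-back mean stays at 35 s. This is one scenario, not a forecast.

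**The case against.** The claims are labelled as proposed. They are not objectives, endpoints or hypotheses, and Sections 8.3.7 and 10 leave analysis detail to a later SAP. That limits the severity, but no analysis detail can supply suture times that were never collected.

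The comparison with the two dropped claims is imperfect. They concerned device dimensions, which this study did not measure at all; here the stapler side is measured and only the comparator is missing. The sponsor's stated reason still carries over to the missing half.

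A reader might infer that the hand-back clock cannot support the under-a-minute claim at all, or counts flaps as closed whether or not they are. The documents do not go that far. Section 8.3.2 titles the item as closure time, the technique in Table 6.1.3-1 includes a visual check of approximation, Section 9.1.2 records delivery success, misfires and staple count are reported, and coaptation is examined at Day 5. A link can be built from these.

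A reader might also infer that the clock favours the device whenever it fails. That direction is not established. Clearing a jam before hand-back lengthens the recorded time, and cases needing sutures may leave the study through Section 7.3.

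Nor do the two operation-time results contradict each other on suturing, because the 64.3-minute group is not a suture group. The closure comparison of 35 against 420 s does favour the stapler. What stands is that the outside evidence is mixed, not that it shows no saving.

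**Conclusion.** The suturing claim does not belong in Section 5.4 as a claim for this study. This follows from the design and needs no assumption. Outside evidence may support some form of it, but that evidence comes from earlier generations, uses different comparators and ranges from 0.4 to 15 minutes.

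The under-a-minute claim is supportable in principle but not by the analysis now planned. It has no 60-second criterion, no link from the recorded time to delivery success or confirmed approximation, and no rule for a second stapler or a conversion. The 11 to 13% of cases over 60 s rests on 8 patients treated with an earlier device and an assumed normal or lognormal shape. It shows why a mean is not enough and does not predict this study's result.

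This should be corrected at low cost; it does not threaten the primary result.

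**What to change.** 1. Section 5.4: delete the suturing claim, or state that it rests on published evidence from earlier device generations. In the second case give the three comparisons from Section 4.2.1 with their comparators.
2. Section 10.4.2: keep the hand-back time, which is an observable event and easier to record consistently than an unblinded operator's judgement of approximation. Add the proportion of all treated subjects with successful delivery and closure time under 60 s, with a Clopper-Pearson 95% interval. Count as not achieved any failed delivery, any conversion to suture, and any second stapler that takes the total over 60 s. Define successful delivery, which the protocol records without defining.
3. State that these cases stay in this denominator and are not dropped through the intra-operative exclusion in Section 7.3. Section 10.2 assigns secondary endpoints to the full analysis and per-protocol sets, so the all-treated set must be named for this analysis.
4. Optionally, report operation time separately for cases with sinus surgery. They are in the full-population summary, but the two named subgroups make no provision for them.

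Cost: wording in Sections 5.4, 10.2 and 10.4.2, and possibly CRF items for a second stapler and for conversion (the CRF is not among the documents). No added patients. One comparative marketing claim is given up or re-attributed, and the under-a-minute figure may come out slightly less favourable.

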# 6. INVESTIGATIONAL PRODUCT(S)

# 6.1 **IDENTIFICATION**

# 6.1.1 Investigation Product

The ENTACT Septal Stapler delivers implantable ENTACT septal staples which are intended to connect internal tissues to aid healing and for approximation of septal flaps of soft tissues during nasal septal surgery. The ENTACT Septal Stapler consists of resorbable fixation devices, which are delivered via a manual surgical stapler delivery system. Each sterile, single patient use device contains eight ENTACT septal staples for holding the septal tissues together during post-op healing.

This document contains information that is confidential and proprietary to Smith + Nephew PLC and Smith + Nephew, Inc. and is intended for use only by Smith + Nephew and its manufacturer. It shall not be reproduced or copied in whole or in part, nor shall the contents be disclosed by any means without prior written permission from Smith + Nephew, nor shall anyone make any use of it that is contrary to the expressed or implied wishes of Smith + Nephew.

Study Protocol	% smith&nephew
A prospective, multi-center, single arm PMCF study to evaluate the safety and performance of ENTACT ™ (Next Generation) resorbable septal staple system for septoplasty	Number: ENTACT.ENT.PRO.SEP.2019.05
	Version: 2.0, 27Aug2020
	Page: Page 28 of 94

The ENTACT staple is designed to resorb in about 3 to 6 weeks when used according to labeling. The staples shown in **Figure 6.1.1-1** are made up of poly(L-lactide-co-glycolide) (PLG), which has an extensive history of use in medical applications. They are biodegradables that degrade into natural compounds found in the body and are easily eliminated through normal physiological pathways.

Figure 6.1.1-1 Staple Implant Configuration (2.5mm X 4.6mm X 0.7mm)

The distal tip of the ENTACT Septal Stapler mechanism shown in **Figure 6.1.1-2** displays the primary mechanical components. The preloaded implants are stacked in a holding block. The most distal implant is deployed by a Nitinol ribbon that is advanced when the trigger is pulled. Once the distal implant has exited the implant holding block, the next implant is indexed into position by the force generated by a spring.

The ENTACT Septal Stapler, with the aid of a piercing needle at the tip of the Nitinol ribbon, is designed to deploy the staple with sufficient force to penetrate the mucoperichondrial tissue, with or without cartilage reinserted. The removable tab is a safety mechanism to restrain the spring tension off the implants during storage and to prevent jamming prior to implantation.

This document contains information that is confidential and proprietary to Smith + Nephew PLC and Smith + Nephew, Inc. and is intended for use only by Smith + Nephew and its manufacturer. It shall not be reproduced or copied in whole or in part, nor shall the contents be disclosed by any means without prior written permission from Smith + Nephew, nor shall anyone make any use of it that is contrary to the expressed or implied wishes of Smith + Nephew.

Study Protocol	>∕smith&nephew
A prospective, multi-center, single arm PMCF study to evaluate the safety and performance of ENTACT ™ (Next Generation) resorbable septal staple system for septoplasty	Number: ENTACT.ENT.PRO.SEP.2019.05
	Version: 2.0, 27Aug2020
	Page: Page 29 of 94

